6.4 STUDY INTERVENTION/EXPERIMENTAL MANIPULATION ADHERENCE

Receipt of Treatment. During home visits, participants return-demonstrate oral hygiene skills. For intervention group participants, we discuss the skills with them and provide tailored feedback for improvement if necessary. Similarly, for care partners, each module includes discussion of the individual's impressions of progress, barriers and challenges and new strategies are developed as needed.

Enactment of Skills. Researchers will systematically assess enactment using data from the smart electronic toothbrush that record the date, time, and duration of use, providing an objective measure of oral hygiene behavior.

To further ensure enactment of skills by the care partner, we will assess the fidelity of the explicitly named behavior change techniques such as goal setting and goal implementation which are part of the scripted intervention using recorded or transcribed care partner coaching sessions and on a random schedule.

6.5 CONCOMITANT THERAPY

6.5.1 RESCUE THERAPY

N/A

7 STUDY INTERVENTION/EXPERIMENTAL MANIPULATION DISCONTINUATION AND PARTICIPANT DISCONTINUATION/WITHDRAWAL

7.1 DISCONTINUATION OF STUDY INTERVENTION/EXPERIMENTAL MANIPULATION

When a participant discontinues from the study intervention, he/she will be withdrawn from the study. Section 7.2 describes the data to be collected if a participant withdraws from the study.

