4.4 END-OF-STUDY DEFINITION

A participant is considered to have completed the study if he or she has completed the baseline assessment, all 4 coaching modules (if applicable), the 3-month study visit, and the final 6-month study visit.

The end of the study is defined as completion of the 6-month follow up visit shown in the Schedule of Activities, Section 1.3.

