7.2 PARTICIPANT DISCONTINUATION/WITHDRAWAL FROM THE STUDY

An investigator may discontinue a participant from the study for the following reasons:

1. Any event or medical condition or situation occurs such that continued collection of follow-up study data would not be in the best interest of the participant or care partner or might require an additional treatment that would confound the interpretation of the study
2. The participant no longer meets the inclusion criteria or meets an exclusion criterion (either newly developed or not previously recognized) that precludes further study participation
3. Death of participant or moving away from study site area
4. Lost to follow-up; unable to contact participant

The reason for participant discontinuation or withdrawal from the study will be recorded on the Discontinuation/Withdrawal Case Report Form (CRF). Participants who sign the informed consent form and are randomized but do not receive the study intervention may be replaced. Participants who sign the informed consent form, and are randomized and receive the study intervention, and subsequently withdraw, or are discontinued from the study, will be replaced if the enrollment window is still open.

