General Approach: The overall goal of this study is to demonstrate the effectiveness of the two intervention strategies (TG1, TG2) against that of CG. The primary outcomes are plaque index, which is quantified as the proportion of sites with plaque deposits on at least less than 1/3 of crown, and gingival index, which is quantified as the proportion of sites with at least some mild inflammation. While the unit of randomization is at the dyad level, the primary outcomes will be evaluated at the individual level. As participants and care-partners contribute repeated measures (at baseline, 3 months and 6 months), we will use a linear mixed modeling approach for the analysis of the primary hypotheses, to account for correlation among repeated measures from the same individual. Analyses for all study outcomes will be conducted according to the intention-to-treat (ITT) principle, where all participants are analyzed according to the group in which they were randomized, irrespective of their receipt of allocated treatment. For our primary analysis we will conduct a

complete case analysis, thus excluding participants who are lost to follow up. As a sensitivity analysis, we will use the strategy of last-observation-carried-forward (LOCF) (thus assuming no change), to impute missing values for participants lost to follow up, if a monotone pattern is demonstrated in complete data. A strategy of LOCF is conservative in that it may bias results towards a null effect, but eliminates bias related to differential dropout, especially in the case where participants with no improvement are less likely to complete follow-up assessments. Statistical analyses will be performed in R version 4.4.0. All statistical tests will be two-sided, and a p-value of < 0.05 will be considered statistically significant.

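### Section 7.1 ends outcome collection when a participant stops the intervention, which contradicts the SAP's intention-to-treat principle

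*Combined protocol and SAP*

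**What the plan says.** Protocol section 7.1 is mandatory and makes no distinction by arm: "When a participant discontinues from the study intervention, he/she will be withdrawn from the study". It then points onward: "Section 7.2 describes the data to be collected if a participant withdraws from the study". Section 7.2 does not in fact list any outcome data. It provides for the reason to be entered on a case report form, and for those who withdraw or are discontinued after receiving the intervention to be replaced while enrollment is open. Neither section mentions month-3 or month-6 plaque or gingival indices.

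Section 7.2 also gives the investigator a discretionary list, introduced by "An investigator may discontinue a participant from the study for the following reasons". Reason 1 includes a situation that "might require an additional treatment that would confound the interpretation of the study". Reason 2 reads: "The participant no longer meets the inclusion criteria or meets an exclusion criterion (either newly developed or not previously recognized) that precludes further study participation".

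Section 4.4 counts a participant as having completed only if all the assessments were done and, where they apply, all four coaching modules. That last condition can bind only in Treatment Group 2 (TG2).

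The SAP (General Approach) adopts intention-to-treat, under which "all participants are analyzed according to the group in which they were randomized, irrespective of their receipt of allocated treatment". The same paragraph makes the primary analysis complete case, leaving out those lost to follow-up. Its only sensitivity analysis is last observation carried forward (LOCF), used if the missingness is monotone. The primary timepoint is month 3 (SAP, Study Design).

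**The concern.** An analysis that disregards whether treatment was received needs outcomes from people who stopped treatment. Section 7.1 removes those people from the study at the moment they stop. The missing values are then produced by the protocol itself and not by loss of contact. No analysis method recovers an index that nobody measured. Replacement restores the head count but substitutes other dyads for those who did not continue.

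The rule also has unequal room to act. Control receives a booklet, so there is little to discontinue. TG2 has four coaching modules, an electronic brush, a log and weekly disclosing tablets. If dyads who find the programme hard are withdrawn and left out, the primary comparison moves from the effect of being assigned the programme towards the effect in those who kept it up. The SAP itself allows that people without improvement may be less likely to finish follow-up.

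**Working it through.** **Step 1. The passages side by side.** Take a TG2 dyad that gives up the intervention at week 6 but would accept a visit at week 12.
- Section 7.1: the dyad is withdrawn.
- Section 7.2: the reason is recorded, and the place is refilled if enrollment is open. No visit is provided for.
- SAP, General Approach: the dyad belongs in the TG2 analysis whatever treatment it received. There is no month-3 value to analyse.
- SAP missing-data rules: both are worded for participants lost to follow-up. Protocol section 7.3 uses that term for people who cannot be contacted. This dyad can be contacted, so its handling is not stated. In practice a complete-case analysis drops it.

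**Step 2. The status table (05/08/24, at the head of the SAP).** Consented: 20 + 20 + 20 = 60. Completed: 18 + 17 + 19 = 54. Not completed: 60 − 54 = 6, or 10%. The totals agree with the table.

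| Arm | Not completed | Share | Exact 95% CI |
|---|---|---|---|
| TG1 | 2/20 | 10% | 1.2 to 31.7% |
| TG2 | 3/20 | 15% | 3.2 to 37.9% |
| Control | 1/20 | 5% | 0.1 to 24.9% |

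**Step 3. Is differential loss shown?** TG2 has 3 of the 6 non-completers, which is half. Under equal risk, the chance that TG2 has 3 or more of 6 is 0.32. Fisher's exact test of TG2 against Control gives p = 0.60, and the three-arm exact test gives p = 0.86. The counts are compatible with chance. With 20 per arm they do not exclude a real imbalance either.

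**Step 4. Illustration of the overstatement.** Let D be the gain over Control among TG2 dyads who continue, s the share who stop before month 3, and k the fraction of the gain that stoppers keep. Assume that stoppers differ from continuers only in this gain and that the Control mean is unaffected by its own losses.
- As-assigned effect = D × [(1 − s) + s × k]
- Overstatement ratio = 1 / [(1 − s) + s × k]
- s = 0.15, k = 0: 1 / 0.85 = 1.18, about 18% too large.
- s = 0.15, k = 0.5: 1 / (0.85 + 0.075) = 1 / 0.925 = 1.08, about 8% too large.

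The 15% is the TG2 non-completion share, used as an assumed stopping rate. The table does not say that these three dyads stopped the intervention or that they lack month-3 data.

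**Step 5. Worst-case bounds.** Each outcome is a proportion of sites between 0 and 1. If every non-completer lacks the month-3 value, the worst-case interval for a difference in means has a width equal to the sum of the two missing fractions.
- TG2 minus Control: 0.15 + 0.05 = 0.20.
- TG1 minus Control: 0.10 + 0.05 = 0.15.

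If outcomes were collected from all 60, both widths would be 0. For a milder case, suppose non-completers are worse than completers by 0.1, 0.2 or 0.3 (an assumed range). If this holds in TG2 only, the complete-case bias is 0.15 times that amount: 0.015, 0.030 or 0.045. If it holds in TG2 and Control alike, it is (0.15 − 0.05) times that amount: 0.010, 0.020 or 0.030.

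**The case against.** The strongest reply is that 54 of 60 dyads completed, so little may be missing, and that most of what could be built on section 7.1 goes beyond the text. Much of this stands.

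- **The effect cannot be estimated.** A reader might infer this. It can be estimated under a missing-at-random assumption and bounded without one, as step 5 shows. What is lost is identification without untestable assumptions.
- **Losses fall mainly on the coached arm.** TG2 has half of six losses, with no reasons or timing. A TG2 dyad with every outcome visit but one missed module may count as not completed, so 3/20 is not shown to be missing outcome data.
- **Section 7.2 removes people as their dementia progresses.** The list is discretionary and the same in every arm, and reason 2 is limited to criteria that preclude further participation. The MoCA and MMSE cut-offs in section 5.1 are guidelines for the entry diagnosis, taken from medical records. Nothing makes the repeated MoCA an eligibility recheck. A new antiplatelet or anticoagulant prescription is likewise something that 7.2 permits the investigator to weigh, not an automatic exit.
- **Dental treatment ends follow-up.** Section 5.3 postpones the study visit after periodontal treatment, including cleaning, and documents dental visits during the active phase.
- **Missing a log entry or a module triggers withdrawal.** Section 7.1 speaks of discontinuing the intervention; no passage says that partial adherence counts.
- **LOCF covers it.** When the last value is the baseline one, LOCF is close to the case in step 4 where stoppers gain nothing. But it is one assumption, applied only if missingness is monotone, and worded for people lost to follow-up. It cannot be checked, because the outcomes that would check it are not collected.

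None of these points removes the conflict between section 7.1 and the SAP's stated principle.

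**Conclusion.** The contradiction is real and rests on the documents' own words. Section 7.1 ends outcome collection at discontinuation, section 7.2 does not restore it, and the SAP claims an analysis that needs those outcomes. Under the planned complete-case analysis, the as-assigned effect is not identified without untestable assumptions.

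The size is not established. The overstatement of about 18% or 8% depends on 15% of TG2 stopping before month 3 and on what stoppers retain. A reader might conclude that the bias favours TG2. That is plausible, because TG2 has the most intervention to stop, but it is not shown: progression, death and other reasons act in all arms. The status table also counts consented dyads and leaves out ineligible ones. Randomization precedes the first visit, where written consent is taken, so the table may not include everyone randomized. Some non-completers may have month-3 data.

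This should be fixed before analysis, because it decides what the primary comparison means.

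**What to change.** Reconcile sections 7.1 and 7.2 with the SAP. State that discontinuing the intervention is recorded but does not by itself end outcome collection. Home Visits 2 and 3 are still sought unless consent to follow-up is withdrawn or the investigator judges that continued data collection is not in the participant's interest. Leave the investigator's discretion in 7.2, and all decisions about stopping the intervention, as they are. In the SAP, state how reachable dyads withdrawn under 7.1 are handled.

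If visits are already over, as the SAP's largely past-tense description of the study suggests:
- tabulate non-completers by arm, reason, timing and available month-3 data, using the discontinuation form;
- keep in the mixed model every outcome that was collected, including month-3 values from dyads who left later;
- describe the complete-case result as an effect in those who continued, not as intention-to-treat.

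The cost is a few visits that were already scheduled or, after the fact, one table and one changed sentence, with the model kept to all available data. The estimated effect may come out smaller.

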7.2 PARTICIPANT DISCONTINUATION/WITHDRAWAL FROM THE STUDY

An investigator may discontinue a participant from the study for the following reasons:

1. Any event or medical condition or situation occurs such that continued collection of follow-up study data would not be in the best interest of the participant or care partner or might require an additional treatment that would confound the interpretation of the study
2. The participant no longer meets the inclusion criteria or meets an exclusion criterion (either newly developed or not previously recognized) that precludes further study participation
3. Death of participant or moving away from study site area
4. Lost to follow-up; unable to contact participant

The reason for participant discontinuation or withdrawal from the study will be recorded on the Discontinuation/Withdrawal Case Report Form (CRF). Participants who sign the informed consent form and are randomized but do not receive the study intervention may be replaced. Participants who sign the informed consent form, and are randomized and receive the study intervention, and subsequently withdraw, or are discontinued from the study, will be replaced if the enrollment window is still open.

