6.3 MEASURES TO MINIMIZE BIAS: RANDOMIZATION AND BLINDING

The study team plans to take numerous steps to ensure a rigorous, unbiased study. Prior to the first visit, the statistician will be blinded when randomizing participant and care partner to study groups.

The procedures for the study visits differ based on which arm of the study a participant is assigned; thus, the research staff is not blind to the participant's assigned group. The randomization group determines which research staff members attend the home visits. The Research staff who conduct the study visits with participants and care partners will be trained to adhere to study procedures and interventions appropriately based on group assignment. The interventionist does not attend the visits for the Control Group and Treatment Group 1, reducing risk of contamination through delivery of in-person coaching. The participants will be recruited from local clinics and the intervention will be conducted at each participant's home, so the chances of contamination between the Treatment groups and the Control group is small.

Blinded randomization assignments will be determined by the statistician at the beginning of the study using a block (by sex) random allocation algorithm generated *a priori* by the statistician assuring there will be equal allocation to arms by site. Because the interventionist does not attend study visits for participants in the Control Group and Treatment Group 1, randomization must be done prior to the first visit.

This is a three-group randomized trial [Treatment Group 1, Treatment Group 2 and the Control Group] using randomization blocks by site to ensure balance within this potential confounder. Each randomization block will be composed of two units male and female in each treatment arm by site and randomization error will be minimized by ensuring that an equal number of all of units are randomized to each group. As minorities are recruited, they will sequentially be assigned to each group. To assess for randomization balance, we will use chi-square tests to examine if there are any statistically significant differences between race, and site by the three groups.

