9.2 SAMPLE SIZE DETERMINATION

Since we will collect data from the predictors [X], mediators [M] and outcomes [Y] at all three time points (baseline, 3 months, 6 months), we will use generalized linear mixed models to account for longitudinal repeated measurements over time to produce sample based inferential effects, which is a group-specific averaged effect size slope over all three time points to estimate each pathway strength.

For the power analyses, we proposed a small to medium effect size of 0.3 for our main outcome analyses without mediators. This was based on a combination of the effect size that is needed to detect what is reasonably thought to be a meaningful change and guidance from our pilot study. Thus, for the main effect we need a minimum of 107 subjects to reach 80% power at a significance level of 0.05. For the sequential mediation models, a sample of 120 provided at least 85% power at a significance level of 0.05. Thus, our target is to have a sample size of 120 to complete the intervention. However, if our attrition rate is higher than originally predicted, the sample size will be increased up to 150.

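### Withdrawal on stopping (7.1), replacement (7.2) and a complete-case primary analysis together take randomised dyads out of the comparison that the SAP calls intention-to-treat, while dyads that stay make up the count

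*Combined protocol and SAP*

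**What the plan says.** Protocol 7.1: "When a participant discontinues from the study intervention, he/she will be withdrawn from the study". It refers to 7.2 for the data to be collected after withdrawal, but 7.2 names only the reason for leaving.

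Protocol 7.2 has two replacement rules. For dyads that received nothing: "Participants who sign the informed consent form and are randomized but do not receive the study intervention may be replaced". For those randomised and treated, the rule is mandatory while recruitment is open: they "subsequently withdraw, or are discontinued from the study, will be replaced if the enrollment window is still open". It does not say how a replacement is allocated, whether there is a cap, or whether the replaced dyad's data stay in the analysis.

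The SAP (General Approach) applies intention-to-treat to all outcomes, "where all participants are analyzed according to the group in which they were randomized, irrespective of their receipt of allocated treatment". The same paragraph makes the primary analysis a "complete case analysis, thus excluding participants who are lost to follow up". Last observation carried forward is a sensitivity analysis, used only if missingness is monotone.

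Protocol 9.2 has a second attrition rule: "if our attrition rate is higher than originally predicted, the sample size will be increased up to 150". The synopsis (1.1) repeats it. Neither place gives the predicted rate.

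**The concern.** Each rule is familiar on its own; the difficulty is how they combine. A dyad that finds the intervention hard to sustain stops, is withdrawn, loses later outcome data, falls out of a complete-case analysis and is replaced by another dyad. The number analysed recovers, but the comparison becomes one between dyads able to stay in their arm.

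The arms do not ask the same of dyads. Only Treatment Group 2 has coaching, and its definition of completion (4.4) includes all four modules. Loss related to the intervention is therefore plausible there, and it is the kind of loss that intention-to-treat is meant to keep in view.

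A second consequence is that the target cannot be interpreted. With two attrition rules and two uses of 120, a reader cannot tell how many dyads were to be randomised, or what retention was assumed.

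**Working it through.** **1. The plan's own figure.** Section 9.2 gives an effect size of 0.3, 80% power, a significance level of 0.05 and a minimum of 107. The effect metric is not stated. Assume Cohen's f and a three-group omnibus test on 2 degrees of freedom. The noncentrality for 80% power is 9.635, and N = 9.635 / 0.3² = 107.05, which matches 107. (The exact F test gives 78.8% power at 107 and needs 111 for 80%.) So 107 is a number analysed, with no allowance for attrition. If 120 are enrolled, 107 remain as long as attrition is no more than 1 − 107/120 = 10.8%.

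**2. One dyad followed through the rules.** Take a dyad assessed at baseline and month 3 that stops before month 6.
- 7.1: it is withdrawn.
- 7.2: its reason is recorded, and it is replaced if enrolment is open.
- SAP: as an incomplete case it is excluded from the primary analysis, along with its month-3 scores. Month 3 is the primary time point in the SAP's Study Design section.
- The SAP's linear mixed model (Aim 1) could use those scores without any new data.

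This reads complete-case as requiring all visits. On a narrower reading only dyads lost to follow-up in the sense of 7.3 (unreachable) are excluded. The SAP does not say which it means.

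**3. Size of the exclusion.** From the accrual table dated 05/08/24:

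| Arm | Consented | Completed | Not completed |
|---|---|---|---|
| Treatment Group 1 | 20 | 18 | 2 (10%) |
| Treatment Group 2 | 20 | 17 | 3 (15%) |
| Control | 20 | 19 | 1 (5%) |
| Total | 60 | 54 | 6 (10%) |

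The table does not say whether the six withdrew, were lost or were still in follow-up, and it does not show replacements.

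**4. Does replacement itself change the bias?** Let those who stay have mean S, let leavers differ from them by d standard deviations, and let p be the fraction leaving an arm. The mean of all randomised dyads is S − p·d and the complete-case mean is S, so the arm is off by p·d. Replacements who stay also have mean S, so the gap remains p·d. Replacement neither causes nor cures it; exclusion does.

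**5. The two attrition rules.** Dyads needed for 120 completers = 120 / (1 − attrition), rounded up:

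| Attrition | Dyads needed |
|---|---|
| 5% | 127 |
| 10% | 134 |
| 15% | 142 |
| 20% | 150 |
| 25% | 160 |

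Replacing every withdrawal therefore stays within 150 up to 20% attrition and exceeds it beyond that. The triggers differ: 7.2 acts on each treated withdrawal, while 9.2 acts only above a predicted rate that is not given. Section 9.2 treats 120 as the number completing. Section 5.5 treats it as the number enrolled, with 680 screened for 120 and 850 for 150 (both 5.67 per dyad enrolled).

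**The case against.** The strongest reply is that enrolling more dyads does not breach intention-to-treat, and that nothing in the documents removes a dyad because it was replaced. That stands. The exclusion comes from the complete-case rule, so deleting the replacement sentences alone would achieve little. It is also true that with 60 consented against a target of 120, a replacement is hard to tell from the next dyad enrolled, and that the 150 ceiling was not approached.

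Four stronger readings are tempting, and the documents do not support them.
- **A replacement takes the vacated slot, so its arm is known in advance.** Section 6.3 aims at "ensuring that an equal number of all of units are randomized to each group" and staff are not blind, but no text says that replacements fill the same slot or arm. If they did, assignment would be predictable. If they take the next entry on the list, it is not certain: best guessing in an unmasked three-arm block is right about 51% to 61% of the time (assumed block sizes 12 to 3), for every enrolment alike. The equal 20/20/20 counts fit ordinary blocking.
- **Six of 60 allocations were foreseeable replacements.** This needs all six non-completers to have withdrawn, been replaced, and been replaced into the same slot. No replacement is recorded.
- **The two attrition rules are incompatible.** They can operate together up to 20% attrition. They are unreconciled.
- **Section 7.2 biases the contrast by 0.05 to 0.10 SD.** That figure is (0.15 − 0.05) × d with d from 0.5 to 1. No document gives d, 15% versus 5% is 3 dyads versus 1, and by step 4 the result is the same with or without replacement.

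**Conclusion.** The point holds as a conflict between the declared principle and the stated primary analysis. Sections 7.1 and 7.2 and the complete-case rule together let dyads that stay stand in for randomised dyads that are excluded. At the reported counts, up to 6 of 60 consented dyads (10%; 2, 3 and 1 by arm) would leave the primary analysis, assuming that none was still in follow-up and that complete-case requires all visits. These counts are too small to establish differential loss, and no size of bias can be attributed to 7.2.

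The silence on how replacements are allocated, the unreconciled 150 rule and the double meaning of 120 are lesser gaps that the same edit can close. The number randomised is itself not shown: randomisation precedes the first visit, where written consent is taken, and the accrual table counts consented dyads without the ineligible.

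The change is worth making although recruitment fell short, because it concerns how data already collected are analysed.

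**What to change.** 1. State in 7.2 and in the SAP's General Approach that all randomised dyads, including any that were replaced, stay in their assigned arm and that all their observed outcome data enter the primary linear mixed model. Keep complete-case as a sensitivity analysis beside the existing one. A dyad seen only at baseline adds little to the 3-month contrast, but one seen at month 3 keeps its primary outcome.
2. State in 7.2 that any dyad enrolled to offset attrition is additional and takes the next unused allocation on the list.
3. Reconcile 7.2 with 1.1 and 9.2 as one attrition rule with a stated predicted rate and cap, and say whether 120 means enrolled or completed. If completed, 10% attrition implies 134 dyads.
4. List any dyads already replaced by arm, date, reason and method of allocation, and show the number randomised in the participant flow.

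The cost is wording in both documents, a listing from the randomisation log and a little more analysis work. No new data are needed. Reported retention will look slightly less favourable.
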